7.3.1 Exposure

The following information on drug exposure will be presented by treatment arm and overall, for the SAF.

Exposure related variables are defined in Section [6.5.4](#)

Descriptive statistics will be produced for:

- The amount of drug (roxadustat and placebo) the subject was exposed to during the treatment period (in mg and in mg/kg), by month, during the first 24, 36, 52 weeks and overall;
- Number and percentage of subjects with dose increases, decreases or interruptions during the treatment period.

Duration of exposure will be summarized in two ways:

- Descriptive statistics will be presented overall, during the first 24 weeks, 36 weeks and 52 weeks;
- Exposure time will be categorized overall, and by treatment period, according to the following categories (and frequency tabulations):
 - Less than 2 weeks
 - At least 2 weeks, less than 4 weeks
 - At least 4 weeks, less than 12 weeks
 - At least 12 weeks, less than 24 weeks

- At least 24 weeks, less than 36 weeks
- At least 36 weeks, less than 52 weeks
- At least 52 weeks, less than 78 weeks
- 78 weeks or more
- Unknown.

Box-plots of monthly dose and monthly dose/kg by month will be produced by treatment arm (roxadustat and placebo).

Study drug medication will also be listed showing for each subject and each visit the dispensed kit numbers and the actual medication in each kit. For instance, if a subject randomized to placebo, at one visit was mistakenly dispensed a kit containing roxadustat then the listing will show that roxadustat was given to the subject on the intended visit.

7.3.2 Treatment Compliance

Overall compliance with the dosing schedule will be examined for subjects in the SAF whose total study drug count and first and last days of treatment are known.

Percent overall compliance will be summarized in two ways, by month, by treatment period, during the first 24 weeks, 36 weeks, 52 weeks and overall:

- Descriptive statistics will be presented,
- Percent compliance categories will be categorized according to the categories defined in Section [6.5.4](#)

Counts and percentages of subjects in each of these categories will be summarized.

Results will be displayed by treatment arm and overall.

7.4 Analysis of Efficacy

For all continuous efficacy variables, in addition to inferential analyses, descriptive statistics will be produced for the actual values and for the changes from baseline (BL) by visit.

Similarly, for all categorical efficacy variables, frequencies and proportions will be produced by analysis visit.

Quantitative endpoints with repeated measures over time will be analyzed using MMRM and ANCOVA with Multiple Imputations (MI) as the preferred methods for imputation of missing data, as per FDA recommendation at the time of SPA assessment of FGCL-4592-060.

For this section, PPS refers to the analysis set which excludes from the FAS all the subjects criteria listed in [Table 3](#). See Section [5.3](#) and Classification specifications for more details.

Analysis visits windows are detailed in Section [7.11.4](#)

Missing data imputation rules are detailed in Section [7.11.1](#)

7.4.1 Analysis of Primary Endpoint(s)

There are two separate regionally based primary efficacy endpoints in this study depending upon whether the data are being filed to support submission to the EU EMA or to ex-EU health authorities, such as the US FDA.

7.4.1.1 EU (EMA) Primary Endpoint

7.4.1.1.1 Primary Analysis of the EU (EMA) Primary Endpoint

The EU (EMA) primary efficacy endpoint will be analyzed using the FAS. See Section [7.11.1](#) for imputation rules, in case of missing values in the evaluation period or in case of rescue therapy prior to Hb response.

The proportion of responders in the primary efficacy variable will be compared using a Cochran–Mantel–Haenszel (CMH) test adjusting for the region, history of CV, baseline Hb and baseline eGFR, comparing roxadustat to placebo.

The EU (EMA) primary hypothesis to be tested for the primary efficacy analysis is:

- H_0 : Hb responder rate in the roxadustat group = Hb responder rate in Placebo group versus
- H_1 : Hb responder rate in the roxadustat group \neq Hb responder rate in Placebo

The CMH adjusted odds ratio (roxadustat versus placebo) and its 95% confidence interval will be provided. Superiority of roxadustat versus placebo will be declared if the lower bound of the two-sided 95% confidence interval of the CMH odds ratio is higher than 1.

The SAS procedure will be similar to the following:

```
proc freq;  
tables covariates*Treatment*Response / cmh;  
run;
```

The covariates will be:

- Region [West Europe, Rest of the World])
- Baseline Hb values (≤ 8 g/dL vs. > 8 g/dL)
- History of cardiovascular, cerebrovascular or thromboembolic diseases (Yes vs. No)
- Baseline eGFR (< 30 mL/min/1.73 m² vs. ≥ 30 mL/min/1.73 m²)

The analysis will use the collected eCRF data to derive these covariates. Note that the choice was made to use Baseline Hb and eGFR as covariates rather than Screening Hb and eGFR which were stratification factors since Baseline values are the latest pre-dose assessments (and no difference between Screening and Baseline is expected).

In addition, a 95% confidence interval for the proportion of each roxadustat and Placebo based on the exact method of Clopper-Pearson will be calculated and presented.

The SAS procedure will be similar to the following:

```
proc freq;
tables Treatment / binomial(exact) alpha=0.05;
run;
```

Model checking

The assumption that the odds ratios are homogeneous across strata will be tested using the Breslow-Day test for stratified 2x2 tables. The model will be checked using covariates above defined by raw data.

In addition, this test will be repeated replacing the covariates by country. For this analysis, countries with less than 20 subjects in the FAS will be pooled in a grouped level per region.

This model checking information will be provided as part of the raw SAS outputs.

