7.4.1.1 Primary Analysis

EU (EMA)

The EU (EMA) primary efficacy endpoint will be analyzed using the FAS.

The proportion of responders in the EU (EMA) primary efficacy endpoint will be compared using a Cochran–Mantel–Haenszel (CMH) test adjusting for the stratification factors comparing pooled roxadustat to pooled placebo. The EU (EMA) primary hypothesis to be tested for the primary efficacy analysis is:

H_0 : Hb responder rate in the roxadustat group = Hb responder rate in the Placebo group

versus

H_1 : Hb responder rate in the roxadustat group \neq Hb responder rate in the Placebo group

H_0 tested at the $\alpha=0.05$ level of significance and will be rejected if the $p<0.05$ from the test.

The CMH adjusted odds ratio (pooled roxadustat versus pooled placebo) and its 95% confidence interval (CI) will be provided. In addition, a 95% CI will be calculated for the proportion of each roxadustat and placebo based on the exact method of Clopper-Pearson.

US (FDA)

The US (FDA) primary efficacy endpoint will be analyzed using all randomized subjects (intent-to-treat principle).

The Hb change from BL to the average Hb of weeks 28-52 will be analyzed using a Mixed Model of Repeated Measurements (MMRM) with unstructured covariance matrix model. The model will contain terms for treatment arm, BL measurement, visit, visit x treatment arm, and other stratification factors.

The primary hypothesis to be tested for the US (FDA) primary efficacy analysis is:

H_0 : Hb mean change from BL to the average level from Week 28 to Week 52 in the roxadustat group = Hb mean change from BL in the placebo group

versus:

H_1 : Hb mean change from BL to the average level of Week 28 to Week 52 in the roxadustat group \neq Hb mean change from BL in the placebo group.

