4 SAMPLE SIZE

A minimum of 450 and up to 600 subjects are planned to be randomized to receive roxadustat or placebo (2:1 with approximately 300 roxadustat versus 150 placebo) in a double-blind manner in order to support the primary endpoint(s) of the study.

EU (EMA)

Three hundred subjects for the roxadustat treatment group and 150 subjects for the placebo treatment group are needed to achieve at least power of 95% to demonstrate a statistically significant difference with a 5% two-sided significance level between roxadustat and placebo in the primary endpoint assuming that the proportion of subjects with response in the roxadustat group is at least 65% and in the placebo group is at most 25%.

USA (FDA)

A sample size of 450 will allow the study to have at least power of 99% to detect a 1.0 g/dL difference in mean Hb values between the two treatment groups, assuming that the common standard deviation is 1.2 g/dL using an analysis of variance (ANOVA) test with a 5% two-sided significance level.

Most importantly, this sample size is required for a meta-analysis of composite safety endpoint by pooling studies. In case the minimum size of four hundred and fifty subjects is not large enough to achieve the required number of MACE/MACE+ events, an increase in the sample size up to 600 is regarded.

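### SAP 7.4.1.1.1: the template code for the per-arm Clopper-Pearson intervals tabulates treatment, not response, and so contradicts its own text

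*SAP*

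**What the plan says.** SAP 7.4.1.1.1 compares the arms on the proportion of responders with a CMH test, and rests superiority on the confidence interval of the CMH odds ratio. The code for that test is "tables covariates*Treatment*Response / cmh", which names both treatment and response.

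The section then adds that "a 95% confidence interval for the proportion of each roxadustat and Placebo based on the exact method of Clopper-Pearson will be calculated and presented". Protocol 7.4.1.1 has the same commitment: "a 95% CI will be calculated for the proportion of each roxadustat and placebo based on the exact method of Clopper-Pearson". Since both sections concern the responder rate, this means two intervals, one per arm.

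The SAP introduces its code with "The SAS procedure will be similar to the following". For the exact interval, the operative line is "tables Treatment / binomial(exact) alpha=0.05". There is no response variable, no BY statement and no subsetting.

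**The concern.** The code and the sentence above it describe different quantities. A one-way table of treatment with the binomial option estimates the fraction of subjects who fall in one treatment level. That fraction is set by the 2:1 randomisation, and changing every subject's response would leave the output unchanged. It is also one interval where the text promises two.

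The intervals at stake are named in the protocol as output for the EU primary endpoint. A programmer who starts from the template would have to change both the variable and the by-arm structure to obtain them. SAP 7.4.1.1.3 asks for subgroup summaries similar to those of the primary analysis, so a reused template would repeat the error in each subgroup.

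**Working it through.** **Inputs**
- Allocation: 2:1, about 300 roxadustat and 150 placebo (SAP 4), up to 400 and 200 (SAP 3.3).
- Planning rates: "roxadustat group is at least 65% and in the placebo group is at most 25" per cent (SAP 4).
- Level: "with a 5% two-sided significance level" (SAP 4).
- Assumption: planned numbers stand in for the FAS, whose realised size the documents do not give.

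**1. The plan's own figure.** The documents state no numerical Clopper-Pearson interval. The nearest stated figure is the power, above 95% (Protocol 7.1). With the pooled-variance normal approximation:
- Pooled rate = (0.65 × 300 + 0.25 × 150) / 450 = 232.5 / 450 = 0.5167.
- SE under the null = √[0.5167 × 0.4833 × (1/300 + 1/150)] = 0.0500.
- SE under the alternative = √[0.65 × 0.35/300 + 0.25 × 0.75/150] = 0.0448.
- z = (0.40 − 1.96 × 0.0500) / 0.0448 ≈ 6.7, so power exceeds 0.9999.

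The stated power is confirmed, so these inputs are read as the plan intends.

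**2. Interval formula.** For x events in n subjects, the Clopper-Pearson limits are the 0.025 quantile of Beta(x, n − x + 1) and the 0.975 quantile of Beta(x + 1, n − x).

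**3. What the code returns.** Here x is the number of subjects in the first treatment level and n is both arms together.

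| First level | N = 450 | N = 600 |
|---|---|---|
| Roxadustat | 300/450 = 66.7% (62.1% to 71.0%) | 400/600 = 66.7% (62.7% to 70.4%) |
| Placebo | 150/450 = 33.3% (29.0% to 37.9%) | 200/600 = 33.3% (29.6% to 37.3%) |

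Which row appears depends on coding. The arm codes A and B in SAP Table 10 put roxadustat first; arm names in alphabetical order put placebo first.

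**4. What the text asks for, at the planning rates.** Here x is responders and n is the arm.

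| Arm | N = 450 | N = 600 |
|---|---|---|
| Roxadustat | 195/300 = 65.0% (59.3% to 70.4%) | 260/400 = 65.0% (60.1% to 69.7%) |
| Placebo | 37/150 = 24.7% (18.0% to 32.4%) or 38/150 = 25.3% (18.6% to 33.1%) | 50/200 = 25.0% (19.2% to 31.6%) |

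Two placebo counts are shown at N = 450 because 25% of 150 is 37.5.

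**5. Two half-fixes that also fail.** Replacing treatment by response without separating the arms gives the pooled rate, 232.5/450 = 51.7%. Separating the arms without naming the responder level can give the non-responder rate, since No sorts before Yes: for roxadustat 105/300 = 35.0%, with limits 100 − 70.4 = 29.6% and 100 − 59.3 = 40.7%.

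**The case against.** The strongest reply is that the code is only a sketch. It is introduced as similar to what will be run, and the CMH block above it uses a placeholder for the covariates, so neither block is a finished program. The prose in both documents specifies the right quantity. This stands: the estimand is not misspecified, and the wrong output arises only if the line is followed without regard to the text.

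A second reply is that inference is untouched. This also stands. The CMH code contains response, and sensitivity analyses S1 to S5 in SAP 7.4.1.1.2 are CMH or logistic analyses of response.

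A reader might infer that the error would pass unnoticed because 66.7% is close to the assumed 65%. The documents do not support that as a general claim:
- The match needs roxadustat to be the first level. With placebo first, the interval of 29.0% to 37.9% excludes the planned 25%.
- It needs a true rate near 65%, which the SAP states as a minimum. Protocol 1.2.2.2 reports 89% and 91% on a similar criterion in phase 2, at 2.0 mg/kg. An observed rate well above 65% would visibly disagree with 66.7%.
- The output would be one table of treatment levels where two arms are expected. SAP 7.4 separately calls for frequencies and proportions of categorical efficacy variables, and SAP 1 schedules a review of data and outputs before hard lock.

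These checks make the error likely to be caught. They do not make the code agree with the text.

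**Conclusion.** The contradiction is real and visible in the line itself. As written, the code returns the allocation share (66.7% or 33.3%, depending on level order) instead of two responder-rate intervals. The figures assume planned numbers and, for the intended intervals, the planning response rates; FAS counts will shift them slightly, but the coded result stays near two thirds or one third.

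The consequence is small. Only the supplementary per-arm intervals, and any subgroup versions built from the same template, are exposed. A reader might infer that the EU primary result is at risk. It is not, because the CMH test, the odds ratio and the superiority rule use separate code that includes response. This is a code-versus-text correction, worth making because the output is specified in the protocol and the remedy is nearly free.

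**What to change.** Replace the block in SAP 7.4.1.1.1 with a sort followed by a by-arm table of response:

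`proc sort; by Treatment; run;`

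`proc freq; by Treatment; tables Response / binomial(exact level='Yes') alpha=0.05; run;`

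BY processing needs the sorted data. The level should match the responder value actually used; Yes follows the Yes/No definition in SAP 6.1.1.1. Make the same correction wherever SAP 7.4.1.1.3 subgroup summaries reuse the template.

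The cost is a few lines of SAP code. No analysis, hypothesis, data collection or sample size changes.

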7.4.1.1.2 Secondary Analyses (sensitivity) of the EU (EMA) Primary Endpoint

Table 12 summarizes all sensitivity analyses to be performed with the EU (EMA) primary endpoint.

Table 12 Primary and sensitivity analyses for the EU (EMA) primary endpoint

Code	Set	Rescue Therapy	Endpoint	Method	Covariates
Primary	FAS	Without rescue therapy	Response	CMH	Region, history of CV, Baseline Hb and Baseline eGFR
S1	All Randomized	Without rescue therapy	Response	CMH	Region, history of CV, Baseline Hb and Baseline eGFR
S2	PPS	Without rescue therapy	Response	CMH	Region, history of CV, Baseline Hb and Baseline eGFR
S3	FAS	Regardless rescue therapy	Response	CMH	Region, history of CV, Baseline Hb and Baseline eGFR
S4	FAS	Without rescue therapy	Response	Logistic	Region, history of CV, Baseline Hb and Baseline eGFR as continuous covariates
S5	FAS*	Without rescue therapy	Response	CMH	Region, history of CV, Baseline Hb and Baseline eGFR

*patients who were randomized after the implementation of protocol v2.0

For the logistic regressions, the odds ratio (roxadustat vs. placebo) and their 95% confidence intervals will be produced, if convergence achieved.

The SAS procedure will be similar to the following:

```
proc logistic;
class treatment region CV_history;
model response = treatment region cv_history baseline_Hb
baseline_eGFR;
run;
```

For all sensitivity analyses, no hypothesis testing will be done, only confidence intervals presented and graphically represented in a forest plot.

If a relevant baseline variable is identified for which a clinically important imbalance exists at baseline between treatment groups, additional sensitivity analysis on the primary endpoint may be performed using a logistic model adjusting for this baseline variable. This will allow the assessment of the impact of these imbalances on the treatment comparisons.

7.4.1.1.3 Additional Analyses of the EU (EMA) Primary Endpoint

The analysis of the EU (EMA) primary endpoint will be repeated by subgroup of interest. For definitions of subgroups of interest, see Section 7.8

For the EU (EMA) primary endpoint, subgroup analyses will be performed using the primary analysis in Table 12. If one of the subgroups is the same as a stratification factor, the factor will be omitted from the model.

Table 13 Additional Analyses of the EU (EMA) Primary Endpoint

Code	Set	Rescue Therapy	Endpoint*	Method	Covariates
A1	FAS	Without rescue therapy	Response by Subgroup	CMH	Region, history of CV, Baseline Hb and Baseline eGFR

* Subgroup: (1) age, (2) sex, (3) region, (4) baseline hemoglobin category, (5) history of CV, (6) Baseline eGFR category (7) Baseline CRP category and (8) Baseline Iron Repletion Status category

Subgroup analysis will be done by producing separate summaries similar to those produced for the primary analysis. In addition, forest plots will be generated per each subgroup showing subgroup factors on the y-axis and CMH adjusted odds ratios and their 95% confidence interval on the x-axis.

The potential existence of subgroup by treatment interaction will be visually inspected.

7.4.1.2 US (FDA) Primary Endpoint

7.4.1.2.1 Primary Analysis of the US (FDA) Primary Endpoint

The US (FDA) primary efficacy endpoint will be analyzed using the All Randomized Set

The change from baseline to the average Hb of weeks 28 to 52 will be computed from an analysis of covariance (ANCOVA) model with multiple imputations (MI), adjusting for covariates (covariates defined below), comparing roxadustat to placebo.

The primary hypothesis to be tested for the US (FDA) primary efficacy analysis is:

H_0 : Hb mean change from baseline to the average level from Week 28 to Week 52 in the roxadustat group = Hb mean change from baseline in the placebo group

versus:

H_1 : Hb mean change from baseline to the average level of Week 28 to Week 52 in the roxadustat group \neq Hb mean change from baseline in the placebo group.

Difference of least square means (roxadustat minus placebo) and its $100 \times (1 - \alpha/2)\%$ confidence interval will be estimated for the change from baseline to the average of weeks 28 to 52. Superiority of roxadustat versus placebo will be considered successful if the lower bound of the two-sided 95% confidence interval of the difference between treatment arms (roxadustat minus placebo) is higher than 0.

The covariates will be:

- Region (West Europe, Ex-Central East Europe)
- Baseline Hb values (continuous)
- History of cardiovascular, cerebrovascular or thromboembolic diseases (Yes vs. No)
- Baseline eGFR (continuous)

The analysis will not use the randomization strata as stratification errors during the randomization process may occur. The analysis will use the collected eCRF data to derive these covariates.

ANCOVA with MI model:

The MI ANCOVA model will be used to compare the roxadustat and placebo groups in a fixed sequence procedure:

The following steps will be used to conduct the primary analysis.

1. Generate 1000 datasets, using seed 654289, where intermittent missing hemoglobin data will be imputed for each treatment relying on non-missing data from all subjects within each treatment group using the Monte Carlo Markov Chain MCMC imputation model with treatment, baseline hemoglobin, baseline eGFR, region, history of cardiovascular, cerebrovascular or thromboembolic diseases and the available non missing hemoglobin for each scheduled Week.
The MCMC statement in the SAS PROC MI procedure with monotone option will be used. As a result, each dataset will only have missing ending data, or a monotone missing data pattern.
2. For each dataset from step 1, missing ending data (hemoglobin up through end of evaluation period) will be imputed using seed 472794. As a result, 1000 imputed complete datasets will be generated.
 - Missing data at Week 1 will be imputed using the regression imputation model with baseline stratification factor, baseline and hemoglobin from Week 1, using the SAS PROC MI procedure with the REGRESSION option in the MONOTONE statement.
 - The SAS PROC MI procedure will use data separately from each treatment subjects to impute the missing data for a specific Week (i.e. only those that need the imputation for the Week). Since subjects from the different treatment groups for that Week are excluded from the step, they will not contribute to the imputation for the Week.
 - Repeat for all other scheduled Weeks sequentially (Week 2 to the end of evaluation period). Subjects whose missing data were imputed for previous Weeks will contribute to the imputation for the current Week.

The regression imputation model includes an intercept and the slopes of the hemoglobin from previous Weeks and the stratification factors.

3. Analyze each imputed dataset using the ANCOVA using the mean of all observed or imputed Hb values within the evaluation period. The model will contain terms for baseline Hb measurement as a covariate and treatment arm and the other randomization stratification factors except screening Hb (≤ 8 vs > 8) as fixed effects.

4. Combine estimates from the results of each of the 1000 ANCOVA runs using SAS PROC MIANALYZE.

Report the results of the least-squares mean estimates of the change from baseline in hemoglobin during the evaluation period, the estimates of treatment effect (e.g., least-squares mean change from baseline in hemoglobin for the treatment group minus the least-squares mean change from baseline in hemoglobin for the placebo group) and the corresponding p-values and 95% CIs during the evaluation period.

All available Hb values will be used for the calculation of the average in weeks 28 to 52, as defined in analysis windows in Section 7.11.4.

Hb imputation rules using MI are detailed in Section 7.11.1.

A forest plot will be generated showing strata on the y-axis and differences in mean changes from BL to the average in week 28-52 and their 95% confidence interval on the x-axis.

Model checking:

Residual plots will be produced showing the following:

- Model residuals in the y-axis and model predictions in the x-axis,
